6.2 ACCESS TO BLINDED TREATMENT ASSIGNMENT

This is an observational study of an assessment tool and involves no blinded treatments.

6.3 COMPLIANCE

This is not applicable since this is an observational study.

7 EXPERIMENTAL PROCEDURES

Procedures in this study will be performed at Screening and on Day 1. Refer to Section 3.2 for the Overall Schedule of Times and Events.

7.1 SCREENING PERIOD (STUDY DAYS -14 TO -1)

A window of up to 14 days is permitted to enroll a subject after Screening. When feasible, Screening assessments should be completed on the same day. Rescreening will be allowed with the Sponsor's Medical Monitor approval. The following assessments for Screening are required prior to initiating the Screening pre-ISWT assessments:

- Informed consent
- Demographics
- Medical history, including PAH history and WHO Functional Class
- AEs (documented from time of informed consent)
- Concomitant medications
- Vital signs (SBP and DBP)
- Assess subject eligibility per inclusion/exclusion criteria

If eligible after the above assessments, the pre-ISWT, ISWT, and ISWT recovery assessments will be conducted. Any significant changes to the subject's medical condition must be documented throughout the course of the study.

7.1.1 *Pre-ISWT*

AEs and concomitant medications will be assessed throughout the study.

The following assessments are required at -15 and 0 minutes prior to activity induction of PAH symptoms:

- PGI-S questions measurements (to be conducted prior to Borg dyspnea score assessment)
- Borg dyspnea score measurement

Pulse oximetry will be started 15 minutes prior to initiating the ISWT and will be performed continuously through the end of recovery during Period 1. The SpO₂ and HR measurements obtained at -15 and 0 minutes (prior to activity) will be recorded in the subject's source documents and eCRF. Subjects receiving supplemental oxygen during the Screening assessment must continue to receive the same flow rate at all subsequent ISWTs. The supplemental oxygen flow rate must be recorded for each activity, as applicable.

Supplemental oxygen therapy must not be introduced for subjects after the Screening assessment, unless there is an urgent medical need in the clinical judgement of the Investigator.

7.1.2 *ISWT*

AEs and concomitant medications will be assessed throughout the study.

The ISWT will be initiated and the following assessments will be performed immediately at the end of the test (within 1 minute of completing):

- PGI-S questions measurements (to be conducted prior to Borg dyspnea score assessment)
- Borg dyspnea score measurement

Pulse oximetry will be performed continuously through the ISWT. The SpO₂ and HR measurements obtained every minute during the ISWT will be recorded in the subject's source documents and eCRF.

For subjects who meet the minimum level of activity (3 shuttles; ie 30 meters) per inclusion criterion #5, site personnel will schedule their appointment time for the Day 1 Visit based on their assigned cohort and sequence (for subjects on inhaled treprostinil).

7.1.3 *ISWT Recovery*

AEs and concomitant medications will be assessed throughout the study.

The following assessments are required every minute for the first 5 minutes of recovery followed by every 5 minutes for the remainder of the 30-minute recovery:

- PGI-S questions measurements (to be conducted prior to Borg dyspnea score assessment)
- Pulse oximetry (SpO₂ and HR measurements)

Vital signs (SBP and DBP) will be measured prior to subject leaving the clinical site.

7.2 STUDY DAY 1

AEs and concomitant medications will be assessed throughout the study.

The following will be confirmed or updated prior to initiating the ISWT:

- Eligibility per inclusion/exclusion criteria
- Medical history, including PAH history and WHO Functional Class
- Enrollment

Subjects assigned to Cohort A and Sequence 1 will follow procedures presented in Sections 7.2.1.1 and 7.2.1.2. Subjects assigned to Cohort A and Sequence 2 will follow procedures presented in Sections 7.2.1.3 and 7.2.1.4.

Subjects assigned to Cohort B will follow procedures presented in Sections 7.2.2.1 and 7.2.2.2.

7.2.1 Cohort A

Cohort A will include subjects who are currently prescribed and using inhaled treprostinil for the treatment of PAH. Subjects will be assigned to 1 of 2 sequences (Section 3.1).

7.2.1.1 Sequence 1/Period 1

The ISWT will be initiated 3 to 4 hours after a subject's previous dose of inhaled treprostinil (expected trough level).

Pre-ISWT

AEs and concomitant medications will be assessed throughout the study.

The following assessments are required (-15 and 0 minutes prior to activity inducement of PAH symptoms):

- PGI-S questions measurements (to be conducted prior to Borg dyspnea score assessment)
- Borg dyspnea score measurement

Pulse oximetry will start 15 minutes prior to initiating the ISWT and will be performed continuously through the end of recovery. The SpO₂ and HR measurements obtained at -15 and 0 minutes (prior to activity) will be recorded in the subject's source documents and eCRF.

ISWT

AEs and concomitant medications will be assessed throughout the study.

The ISWT will be initiated and the following assessments will be performed immediately at the end of the test (within 1 minute of completing):

- PGI-S questions measurements (to be conducted prior to Borg dyspnea score assessment)
- Borg dyspnea score measurement

Pulse oximetry will be performed continuously throughout. The SpO₂ and HR measurements obtained every minute during the ISWT will be recorded in the subject's source documents and eCRF.

ISWT Recovery

AEs and concomitant medications will be assessed throughout the study.

The following assessments are required every minute for the first 5 minutes of recovery followed by every 5 minutes for the remainder of the 30-minute recovery:

- PGI-S questions measurements
- Pulse oximetry (SpO₂ and HR measurements)

Rest Period

Subjects will be provided at least a 1-hour period for rest between ISWTs (until subject feels they are rested enough to perform again at their baseline level) prior to Period 2 assessments.

The start and end times for this period should be documented in the subject's source documents and eCRF. AEs and concomitant medications will be assessed throughout this period.

7.2.1.2 Sequence 1/Period 2

The ISWT will be initiated within approximately 30 minutes of the previous inhaled treprostinil dose (expected peak level).

Pre-ISWT

AEs and concomitant medications will be assessed throughout the study.

The following assessments are required (-15 and 0 minutes prior to activity inducement of PAH symptoms):

- PGI-S questions measurements (to be conducted prior to Borg dyspnea score assessment)
- Borg dyspnea score measurement

Pulse oximetry will start 15 minutes prior to initiating the ISWT and will be performed continuously through the end of recovery. The SpO₂ and HR measurements obtained at -15 and 0 minutes (prior to activity) will be recorded in the subject's source documents and eCRF.

ISWT

AEs and concomitant medications will be assessed throughout the study.

The ISWT will be initiated and the following assessments will be performed immediately at the end of the test (within 1 minute of completing):

- PGI-S questions measurements (to be conducted prior to Borg dyspnea score assessment)
- Borg dyspnea score measurement

Pulse oximetry will be performed continuously throughout. The SpO₂ and HR measurements obtained every minute during the ISWT will be recorded in the subject's source documents and eCRF.

ISWT Recovery

AEs and concomitant medications will be assessed throughout the study.

The following assessments are required every minute for the first 5 minutes of recovery followed by every 5 minutes for the remainder of the 30-minute recovery:

- PGI-S questions measurements
- Pulse oximetry (SpO₂ and HR measurements)

7.2.1.3 Sequence 2/Period 1

The ISWT will be initiated within approximately 30 minutes of the previous inhaled treprostinil dose (expected peak level).

Pre-ISWT

AEs and concomitant medications will be assessed throughout the study.

The following assessments are required (-15 and 0 minutes prior to activity inducement of PAH symptoms):

- PGI-S questions measurements (to be conducted prior to Borg dyspnea score assessment)
- Borg dyspnea score measurement

Pulse oximetry will start 15 minutes prior to initiating the ISWT and will be performed continuously through the end of recovery. The SpO₂ and HR measurements obtained at -15 and 0 minutes (prior to activity) will be recorded in the subject's source documents and eCRF.

ISWT

AEs and concomitant medications will be assessed throughout the study.

The ISWT will be initiated and the following assessments will be performed immediately at the end of the test (within 1 minute of completing):

- PGI-S questions measurements (to be conducted prior to Borg dyspnea score assessment)
- Borg dyspnea score measurement

Pulse oximetry will be performed continuously throughout. The SpO₂ and HR measurements obtained every minute during the ISWT will be recorded in the subject's source documents and eCRF.

ISWT Recovery

AEs and concomitant medications will be assessed throughout the study.

The following assessments are required every minute for the first 5 minutes of recovery followed by every 5 minutes for the remainder of the 30-minute recovery:

- PGI-S questions measurements
- Pulse oximetry (SpO₂ and HR measurements)

Rest Period

Subjects will be provided at least a 1-hour period for rest between ISWTs (until subject feels they are rested enough to perform again at their baseline level) prior to Period 2 assessments. The start and end times for this period should be documented in the subject's source documents and eCRF. AEs and concomitant medications will be assessed throughout this period.

7.2.1.4 Sequence 2/Period 2

The ISWT will be initiated 3 to 4 hours after a subject's previous dose of inhaled treprostinil (expected trough level).

Pre-ISWT

AEs and concomitant medications will be assessed throughout the study.

The following assessments are required (-15 and 0 minutes prior to activity inducement of PAH symptoms):

- PGI-S questions measurements (to be conducted prior to Borg dyspnea score assessment)
- Borg dyspnea score measurement

Pulse oximetry will start 15 minutes prior to initiating the ISWT and will be performed continuously through the end of recovery. The SpO₂ and HR measurements obtained at -15 and 0 minutes (prior to activity) will be recorded in the subject's source documents and eCRF.

ISWT

AEs and concomitant medications will be assessed throughout the study.

The ISWT will be initiated and the following assessments will be performed immediately at the end of the test (within 1 minute of completing):

- PGI-S questions measurements (to be conducted prior to Borg dyspnea score assessment)
- Borg dyspnea score measurement

Pulse oximetry will be performed continuously throughout. The SpO₂ and HR measurements obtained every minute during the ISWT will be recorded in the subject's source documents and eCRF.

ISWT Recovery

AEs and concomitant medications will be assessed throughout the study.

The following assessments are required every minute for the first 5 minutes of recovery followed by every 5 minutes for the remainder of the 30-minute recovery:

- PGI-S questions measurements
- Pulse oximetry (SpO₂ and HR measurements)

7.2.2 Cohort B

7.2.2.1 Period 1

The ISWT will be initiated approximately 4 hours after the subject's morning dose of PAH medication.

Pre-ISWT

AEs and concomitant medications will continue to be assessed throughout the study.

The following assessments are required (-15 and 0 minutes prior to activity inducement of PAH symptoms):

- PGI-S question measurements (to be conducted prior to Borg dyspnea score assessment)
- Borg dyspnea score measurement

Pulse oximetry will start 15 minutes prior to initiating the ISWT and will be performed continuously through the end of recovery. The SpO₂ and HR measurements obtained at -15 and 0 minutes (prior to activity) will be recorded in the subject's source documents and eCRF.

ISWT

AEs and concomitant medications will be assessed throughout the study.

The ISWT will be initiated and the following assessments will be performed immediately at the end of the test (within 1 minute of completing):

- PGI-S questions measurements (to be conducted prior to Borg dyspnea score assessment)

- Borg dyspnea score measurement

Pulse oximetry will be performed continuously throughout. The SpO₂ and HR measurements obtained every minute during the ISWT will be recorded in the subject's source documents and eCRF.

ISWT Recovery

AEs and concomitant medications will be assessed throughout the study.

The following assessments are required every minute for the first 5 minutes of recovery followed by every 5 minutes for the remainder of the 30-minute recovery:

- PGI-S questions measurements
- Pulse oximetry (SpO₂ and HR measurements)

Rest Period

Subjects will be provided at least a 1-hour period for rest between ISWTs (until subject feels they are rested enough to perform again at their baseline level) prior to Period 2 assessments. The start and end times for this period should be documented in the subject's source documents and eCRF. AEs and concomitant medications will be assessed throughout this period.

7.2.2.2 Period 2

The ISWT will be initiated at least 1 hour after completion of the previous ISWT.

Pre-ISWT

AEs and concomitant medications will continue to be assessed throughout the study.

The following assessments are required (-15 and 0 minutes prior to activity inducement of PAH symptoms):

- PGI-S questions measurements (to be conducted prior to Borg dyspnea score assessment)
- Borg dyspnea score measurement

Pulse oximetry will start 15 minutes prior to initiating the ISWT and will be performed continuously through the end of recovery. The SpO₂ and HR measurements obtained at -15 and 0 minutes (prior to activity) will be recorded in the subject's source documents and eCRF.

ISWT

AEs and concomitant medications will continue to be assessed throughout the study.

The ISWT will be initiated and the following assessments will be performed immediately at the end of the test (within 1 minute of completing):

- PGI-S questions measurements (to be conducted prior to Borg dyspnea score assessment)
- Borg dyspnea score measurement

Pulse oximetry will be performed continuously throughout. The SpO₂ and HR measurements obtained every minute during the ISWT will be recorded in the subject's source documents and eCRF.

ISWT Recovery

AEs and concomitant medications will continue to be assessed throughout the study.

The following assessments are required every minute for the first 5 minutes of recovery followed by every 5 minutes for the remainder of the 30-minute recovery:

- PGI-S questions measurements
- Pulse oximetry (SpO₂ and HR measurements)

7.2.3 Discharge

If the subject permanently discontinues the study prior to completion of all study assessments, for any reason, the following assessments, which are also performed prior to discharge, should be conducted, if possible:

- Vital signs (SBP and DBP)
- AEs
- Concomitant medications

Following completion of all study procedures and once the Investigator deems that the subject has returned to their baseline status, per pulse oximetry readings, the subject will be discharged from the clinic.

8 STUDY TERMINATION

8.1 CRITERIA FOR SUBJECT WITHDRAWAL

A subject may voluntarily withdraw from the study at any time for any reason. A withdrawal of consent would preclude data collection regarding that subject after the date of withdrawal.

In the event a subject discontinues prematurely due to an AE, the subject will be followed until either the Investigator determines that the AE has resolved, it is no longer considered clinically significant, the subject is lost to further follow-up, or for 7 days if the AE extends beyond the final visit. A Subject Discontinuation Form must be completed for all subjects discontinued from the study.

8.2 CRITERIA FOR TERMINATING THE STUDY

The study may be stopped at any time if, in the opinion of the Sponsor, continuation of the study represents a serious medical risk to the subjects. This may include, but is not limited to, the presence of serious, life-threatening, or fatal AEs or AEs that are unacceptable in nature, severity, or frequency. The Sponsor reserves the right to discontinue the study for any reason at any time.

8.3 CRITERIA FOR DISCONTINUING A SITE

The study may also be terminated at a given site if any of the following occur:

- The Principal Investigator elects to discontinue the study
- The Sponsor elects to discontinue the study at the site
- US FDA regulations are not observed
- Concerns with protocol violations
- Changes in personnel or facilities adversely affect performance of the study

9 ADVERSE EVENT REPORTING

All AEs/SAEs that occur while the subject is participating in the study will be recorded as instructed in Section [9.2](#).

9.1 DEFINITIONS

9.1.1 *Adverse Event*

An AE is any untoward or unfavorable medical event experienced by a subject during a clinical study. An AE may include an intercurrent illness, injury, or any other concomitant impairment of the subject's health if deemed to have clinical significance. Adverse events may also include worsening of pre-existing symptoms or conditions that occur as a result of protocol-mandated procedures.

9.1.2 *Serious Adverse Event*

An SAE is an AE that results in any of the following outcomes:

- Death
- A life-threatening AE
- Inpatient hospitalization or prolongation of existing hospitalization
- A persistent or significant disability/incapacity
- A congenital anomaly/birth defect

In addition, important medical events that may not result in death, be life-threatening, or require hospitalization may be considered serious when, based upon appropriate medical judgment, they jeopardize the subject and require medical/surgical intervention to prevent any of the outcomes listed above.

Life-threatening means that the subject was at immediate risk of death from the event as it occurred. It does not mean that the event, had it occurred in a more severe form, might have caused death.

9.2 DOCUMENTATION OF ADVERSE EVENTS

All AEs will be documented from time of informed consent until the subject discontinues or subject completes the study. An AE or SAE occurring during the study must be documented in the subject's source documents and on the appropriate eCRF page(s). Information relating to the AE, such as onset and cessation date and times, intensity, seriousness, and outcome, is also to be documented in the eCRF (see Appendix 15.4 for definitions). Where possible, AEs should be recorded using standard medical terminology. If several signs or symptoms are

clearly related to a medically defined diagnosis or syndrome, the diagnosis or syndrome should be recorded on the eCRF page, not the individual signs and symptoms.

9.3 FOLLOW UP OF ADVERSE EVENTS

In the event a subject discontinues prematurely due to an AE, the subject will be followed until either the Investigator determines that the AE has resolved, it is no longer considered clinically significant, the subject is lost to further follow-up, or for 7 days if the AE extends beyond the final visit.

Follow-up of AEs and SAEs considered related (either possible or probable) to inhaled treprostinil will be processed as a post-marketing case.

9.4 REPORTING RESPONSIBILITIES OF THE INVESTIGATOR

All SAEs, as defined in Appendix 15.4, must be reported using the SAE report form via e-mail or fax within 24 hours of the investigator's knowledge of the SAE occurrence:

- Email to [contact] (primary method)
- Fax to [contact] (back-up method)

The Investigator or Sponsor (if appropriate) must also notify their Institutional Review Board (IRB), Independent Ethics Committee (IEC), and/or other local equivalent agency of the reported SAE, including any follow-up information. Copies of each report and documentation of IEC/IRB/local equivalent body notification and receipt will be kept in the Investigator's study file.

9.5 SAFETY REPORTS

Any SAE that is possibly or reasonably attributable to concomitant PAH treatment (inhaled treprostinil) will be processed as a post-marketing case and requires immediate notification via email to [contact] (primary) or via fax at [contact] (back-up) using the SAE report form.

10 STATISTICAL CONSIDERATIONS

This section briefly describes the planned statistical analyses. A complete description of the methodology will be specified in the Statistical Analysis Plan (SAP), which will be finalized

prior to database lock. Any changes in the statistical methods described in this protocol that occur prior to database lock will be documented in the SAP and will not require a protocol amendment.

10.1 DATA PROCESSING

The results of assessments will be transcribed into an eCRF for each subject who signs an ICF until study completion, or study discontinuation for any reason. A representative from the Sponsor will verify eCRF data fields against source documentation. Data clarifications will be generated, and the database will be edited as appropriate. The eCRFs will be reviewed by the Investigator for completeness and accuracy. The Investigator must electronically sign each subject's eCRF to signify his/her approval of the data. The Investigator will be required to re-sign an eCRF if changes are made to a subject's eCRF by the site after the Investigator initially signs the eCRF. The database will be final when all data management and quality assurance procedures are complete.

10.2 SAMPLE SIZE

Approximately 40 subjects will be enrolled to ensure at least 36 evaluable subjects complete the study. A sample size of 36 is expected to provide sufficient power in the context of this study to evaluate change in the PGI-S items. Assuming a change from baseline endpoint with values that may range between -4 and 4, a common standard deviation as the 50th percentile of the range (~2 units) for each PGI-S item, a correlation between post-activity and baseline measurements of 0.75, and a standard deviation of the difference scores as ~1.3, a 2-sided 95% confidence interval for a paired mean difference, based on the large sample z statistic, will extend approximately 0.52 units. With a confidence interval length at the mid-point of PGI-S response ratings, reasonable confidence in the point estimates observed for the PGI-S items should be achieved.

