5.1 OBSERVATIONAL ENDPOINTS

5.1.1 *Patient Global Impression of Severity*

The primary objective is to characterize the psychometric properties and performance of the 3 PGI-S items, measuring overall PAH symptoms, shortness of breath, and physical fatigue during pre-ISWT, at the end of activity, and through recovery.

The focus of each item, separately, will be the subject's evaluation of:

1. Overall PAH Symptoms: [REDACTED]
2. Shortness of Breath: [REDACTED]
3. Physical Fatigue: [REDACTED]

Subjects will be asked to rate each item based on their level of symptom severity "at this moment" using a 5-point ordinal response scale (1=Not present, 2=Mild, 3=Moderate, 4=Severe, 5=Very severe). The timing of the assessments for Overall PAH Symptoms, Shortness of Breath, and Physical Fatigue scales will be at Screening/Baseline (-15 minutes and at 0 minutes

prior to activity-inducement of PAH symptoms), at completion of the ISWT, and every 1 minute for 5 minutes then every 5 minutes following completion of the ISWT during recovery. The average recovery time of symptoms is unknown but, based on clinician advice, it is expected that recovery should be within 15 to 20 minutes. Assessments for PGI-S will occur for 30 minutes following completion of the ISWT to ensure that the full recovery profile is captured across all subjects observed.

For each PGI-S item, a change from Baseline score will be calculated for the PGI-S items measured from the start of the activity-inducement of PAH symptoms.

5.1.2 *Modified Borg Dyspnea Score*

The Modified Borg Dyspnea score (see Section 9) will be completed by subjects as follows: Subjects will be asked to rate dyspnea “at this moment” on an 11-point numeric rating scale (0=Nothing at all, 10=Maximal) at Screening/Baseline (-15 minutes and at 0 minutes prior to activity-inducement of PAH symptoms) and at completion of the ISWT.

5.1.3 *Oxygen Saturation and Heart Rate*

Oxygen saturation and HR will be measured continuously throughout the observation period with measurements extracted and recorded into eCRFs at Screening/Baseline (-15 minutes and at 0 minutes prior to activity-inducement of PAH symptoms), each minute during the ISWT, at completion of the ISWT, and every 1 minute for 5 minutes then every 5 minutes following completion of ISWT during recovery. Key measurements used for analysis will be those that correspond to the measurement of the PGI-S and Borg Dyspnea scores.

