6.13.2 Response Frequency Distributions

To examine floor and ceiling effects for each PGI-S item, the percentage of subjects reporting the worst and best possible item scores will be examined in the context of the item-level response frequency distributions. A floor effect occurs if the worst response category (5=Very severe) is the mode of the empirical distribution and at least 2 times the expected percentage of subjects (given a uniform distribution) who select this response category. Similarly, a ceiling effect occurs if the best response category (Not present) is the mode of the empirical distribution and at least 2 times the expected percentage of subjects (given a uniform distribution) who select this response category. In the case of the PGI-S items, which have 5 response categories, the expected percentage of subjects given a uniform distribution is 20%; a floor or ceiling effect would require that more than 40% of the subjects select the worst or best response category, respectively.

PGI-S response frequency distributions will be tabulated and examined at Baseline (pre-ISWT average of -15 minutes and 0 minutes), when symptoms are expected at their minimal level, and post-ISWT (0 minutes), when symptoms are expected at their maximum level. Distributions will be provided for all subjects and visits/periods combined, as well as individually within Cohorts and visits/periods (Screening, Day 1 Period 1, and Day 1 Period 2).

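### The planning SD of about 2 for each PGI-S item is the ceiling of a 1-to-5 scale and does not fit minimal resting symptoms, so the expected interval width is overstated

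*Protocol*

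**What the plan says.** Protocol 10.2, repeated in substance in SAP 4, gives one paragraph of justification: "Approximately 40 subjects will be enrolled to ensure at least 36 evaluable subjects complete the study". Its inputs are:

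- the endpoint: "Assuming a change from baseline endpoint with values that may range between -4 and 4";
- the spread: "a common standard deviation as the 50th percentile of the range (~2 units) for each PGI-S item";
- the correlation: "a correlation between post-activity and baseline measurements of 0.75";
- the spread of change: "a standard deviation of the difference scores as ~1.3".

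The result is that "a 2-sided 95% confidence interval for a paired mean difference, based on the large sample z statistic, will extend approximately 0.52 units".

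Three places in the SAP bear on whether that spread is possible. SAP 5.1.1 scores each item on a "5-point ordinal response scale (1=Not present, 2=Mild, 3=Moderate, 4=Severe, 5=Very severe"). SAP 6.13.2 describes baseline as the time "when symptoms are expected at their minimal level", and 0 minutes after the walk as the time of the maximum. SAP 6.11.1 takes a one-category change as meaningful. The item wording in the protocol appendix is redacted, so the 1-to-5 scoring comes from the SAP. It agrees with the protocol's change range of -4 to 4.

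**The concern.** A bounded score cannot have an arbitrarily large SD, and an SD close to the limit is possible only if answers pile up at both ends of the scale. A planning SD of about 2, common to rest and to the end of the walk, would mean many subjects answering Very severe while sitting still. It would also leave little room for the average score to rise. The study expects the opposite: low scores at rest and a clear increase after exertion.

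This paragraph is the only support for the statements that 36 subjects are sufficient and that the point estimates will be reasonably precise. If its spread cannot occur in the population described, the stated precision is not a usable forecast, either overall or for the comparisons within one cohort, for which no precision is given.

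**Working it through.** **Inputs.** From Protocol 10.2: n = 36, common SD about 2, correlation 0.75, SD of differences about 1.3, two-sided 95% z interval. From SAP 5.1.1: scores 1 to 5. From SAP 6.3.2: baseline is the mean of the -15 and 0 minute scores, which stays between 1 and 5.

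**The plan's own figure.** Half-width = 1.96 × SD of differences / √n.

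- SD of differences 1.3: 1.96 × 1.3 / 6 = 0.42 (full width 0.85).
- SD of differences derived from SD 2 and correlation 0.75: √(2 × 4 × 0.25) = 1.41, so 1.96 × 1.41 / 6 = 0.46 (full width 0.92).

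Neither gives 0.52. At n = 36, 0.52 would need an SD of differences of 0.52 × 6 / 1.96 = 1.59. That is a separate arithmetic fault, which the same rewrite would remove. The inputs also disagree slightly: SD of differences 1.3 with correlation 0.75 implies a common SD of 1.3 / √(2 × 0.25) = 1.84. I use 1.84 below because it is the reading of about 2 most favourable to the plan.

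**Ceiling.** For a score between 1 and 5 with mean m, variance ≤ (m − 1)(5 − m). The maximum is 4, at m = 3, so SD ≤ 2. Equality needs half the subjects at 1 and half at 5.

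**What the SD requires at rest.** An SD of s forces the mean into 3 ± √(4 − s²). For s = 1.84: √(4 − 3.386) = 0.784, so the resting mean is at least 2.22. The distribution at that limit uses only the end categories, with a share (2.22 − 1)/4 = 0.30 at 5. A linear-programming search over all distributions on the scale, with half-points allowed for the averaged baseline, confirms that at least 30% must score 4 or more.

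**What it allows as mean change.** The same kind of search ran over joint distributions with equal SDs and correlation 0.75:

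| Common SD | Each mean within 3 ± | Largest mean change |
|---|---|---|
| 2.00 | 0 | 0 |
| 1.95 | 0.44 | about 0.60 |
| 1.90 | 0.62 | about 0.70 |
| 1.84 | 0.78 | about 0.80 |
| 1.75 | 0.97 | about 0.95 |
| 1.50 | 1.32 | about 1.40 |

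At an SD of 1.75 or more, a mean change of one full category is out of reach.

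**Size of the effect on precision (assumed distributions).** Suppose 70/25/5% in categories 1/2/3 at rest (variance 0.3275, SD 0.57) and 5/25/40/25/5% in categories 1 to 5 at completion (variance 0.90, SD 0.95). SD of change = √(0.3275 + 0.90 − 2 × ρ × 0.572 × 0.949).

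- ρ = 0.75: SD of change 0.64; half-width at n = 36 is 1.96 × 0.64 / 6 = 0.21.
- ρ = 0.25: SD of change 0.98; half-width 1.96 × 0.98 / 6 = 0.32.

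**Single-cohort comparisons.** SAP 6.11.2 and 6.11.3 compare the change scores between periods within one cohort. Protocol 5.2 enrols equal cohorts, so n is about 18. The SD needed is SD(change) × √(2(1 − r)), where r is the between-period correlation of the change scores. With t = 2.11 on 17 degrees of freedom, half-width = 2.11 × SD(change) × √(2(1 − r)) / √18. For SD(change) of 0.64 to 0.98 this is 0.45 to 0.69 at r = 0, 0.32 to 0.49 at r = 0.5, and 0.23 to 0.34 at r = 0.75. These values of r are assumptions; the documents give none.

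**The case against.** The strongest reply is that the calculation is for an interval width. No mean or mean change enters it, so any constraint on the means does not alter the result. A spread set too high makes the planned interval wider than the one the study is likely to deliver, which is the safe direction. All of this stands, and it is why the point does not touch the sample size.

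A reader might go further and infer that the plan describes a study with no symptom change, since an SD of 2 at both times puts both means at 3. The documents do not support that. They say about 2, and the result holds only at exactly 2. The plan's own SD of differences and correlation imply 1.84, which allows a mean change of up to about 0.8. What survives is narrower: throughout a reasonable reading of about 2, the SD conflicts with minimal resting symptoms and leaves room for less than a one-category mean change.

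It is also fair to read the percentile phrase as clumsy wording for half of a four-point range. The intended value is printed beside it, so nothing is rested on the phrase.

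**Conclusion.** The planning SD is wrong as written. It sits at the mathematical ceiling of the scale. Even at 1.84 it needs a resting mean of at least 2.22 and at least 30% of subjects Severe or Very severe at rest, against SAP 6.13.2, and it caps the mean change at about 0.8, against the one category in SAP 6.11.1. These bounds rest only on the 1-to-5 scoring, equal SDs and the stated correlation.

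The consequence is an overstated interval width. Under the assumed distributions the half-width at n = 36 is 0.21 to 0.32 rather than 0.52; part of that gap is the separate arithmetic fault, since the plan's inputs give 0.42 to 0.46. The size of the overstatement depends on the assumed SDs, for which the documents offer no data. A reader might take the faulty input as evidence that 36 is too few. It is not: the error runs in the conservative direction for the overall pre-to-post change. For the single-cohort comparisons the documents state no precision at all, and it depends on a correlation they do not give.

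**What to change.** In Protocol 10.2 and SAP 4:

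1. Replace the common SD of about 2 with separate resting and completion SDs that the 1-to-5 scale and the expected low resting level allow. Label them as assumptions and give a range; the 0.57 and 0.95 used above are only an illustration.
2. Derive the SD of change from those SDs and the correlation, instead of stating it independently.
3. Restate the half-width for n = 36, and say that it is a half-width.
4. For SAP 6.11.2 and 6.11.3 (n about 18), add a half-width based on SD(change) × √(2(1 − r)) over a stated range of the between-period correlation r. Using the SD of change alone would be right only at r = 0.5.

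Keep the sample size. The cost is a text change in two places, with no extra subjects, visits or data. SAP 1 says that the SAP supersedes the protocol's statistical considerations, so if the protocol is not being amended for other reasons, the correction can be made in SAP 4 with a note that it replaces Protocol 10.2.
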